	
Behavior Index and its subscales (Internalizing, Externalizing)
 
Exploratory efficacy endpoint
 
 • Slope estimate from the linear regression of GCA scores over time for each subject 
Additional efficacy endpoint for substudy only
 
 • Observed value in raw score, age equivalents versus chronological age, as well as DQ, composite score and percentile for the three scales of the BSID-III (Motor [Fine, Gross], Language [Receptive, Expressive], Cognitive) for substudy only 
Pharmacokinetic and Pharmacodynamic endpoints
 
 • Serum concentration of idursulfase and serum PK parameters after IT administration • CSF concentration of idursulfase prior to each monthly IT administration • Change from baseline in the concentration of GAG in CSF 
Safety Assessments
 
Safety will be assessed during the study by collection of adverse events (by type, severity, and relationship to treatment [idursulfase-IT, the IDDD, device surgical procedure, or IT administration process] and IV Elaprase infusion), changes in clinical laboratory testing (serum chemistry, hematology, urinalysis), physical and neurological examination, vital signs, 12-lead ECG, CSF laboratory parameters (chemistries, cell counts), anti-idursulfase antibodies in CSF and serum, and determination of antibodies having enzyme neutralizing activity.
 
SOPH-A-PORT[®] Mini S Device Assessments
 
The SOPH-A-PORT Mini S device will be evaluated using assessments of device implantation, device function, device longevity and adverse events associated with the implant surgery or device. Those data will be collected on the patient's electronic case report form (eCRF) from the time of initial implantation and continue throughout the study as long as the SOPH-A-PORT[®] Mini S remains implanted.
 
Health Status Assessment
 
Health status dimensions as obtained by the EQ-5D questionnaire: mobility, self-care, usual activities, pain/discomfort, and anxiety/depression.

Number of Subjects	
Pivotal study
 
 • 48 male patients (32 IT treated and 16 No IT treatment) are planned.

	
Substudy
 
 • There is no pre-specified number of patients planned. The enrollment will conclude when enrollment of patients in the pivotal study closes.

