4.2 Determination of Sample Size/Randomization

Based on study HGT-HIT-050/045 Phase I/II data, the observed decline in mean General Conceptual Ability (GCA) standard score (SS) in No IT treatment patients was estimated to be 13.7 points with a standard deviation of 9.4 after 12 months. For the sample size calculation, we conservatively assumed an approximately 1 point per month rate of decline in the No IT treatment arm, so that the theoretical decline would be 13 points from baseline (Screening Visit) to Visit Week 52 (~ 13 months). As up to 2 months may elapse between the screening assessment and the start of idursulfase-IT treatment, a mean decline of 2 points at end of study would be expected if idursulfase was effective in stabilizing the decline. Therefore, in such a case, the mean projected treatment difference at Visit Week 52 would be 11 points, which is considered a clinically meaningful treatment difference.

Using a 2:1 allocation ratio, a sample size of 48 randomized patients (about 32 IT treated patients and 16 no IT treatment patients) will yield 80% power to detect a clinically meaningful mean treatment difference of 11 points in the primary endpoint, GCA change from baseline to Visit Week 52. This calculation further assumes a common standard deviation for the change from baseline of 11.6 points, a type-I error rate of 0.05 for a two-sided two-sample t-test, with approximately up to 10% missing an assessment at Visit Week 52. Given this sample size, and conditional on rejection of the null hypothesis for the primary endpoint, the power would be 80% to detect a clinically meaningful mean difference of 10 points in the key secondary endpoint, change from baseline in ABC standard score at Visit Week 52, assuming a standard deviation for the change from baseline of 10.5 points for a two-sided two-sample t-test with a significance level of 5% and 10% missing an assessment at Visit Week 52.

The variance estimate for this sample size was determined based on a blinded variability assessment (BVA) performed as specified in the prior protocol version (Amendment 3); refer to

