6.7.5.4 Rate of Change in GCA Score Analysis

The endpoint of rate of change analysis is the slope estimate from the linear regression of GCA score over time for each subject. Only subjects with at least 3 available GCA scores will be included in this analysis.

The slope estimate will be compared between the two treatment groups in HIT-HGT-094 using one-way ANOVA. The response variable in the ANOVA model is the weighted linear regression slope, where the weight is the inverse of one plus the sum of mean squared error (MSE) from the linear regression, i.e. $1/(1+\text{MSE})$.

The sample SAS code is presented in [appendix 9.2.5](#).

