The sample SAS code is presented in the [appendix 9.2.6](#).

The multiplicity adjustment for the primary and secondary endpoints is shown in the following flowchart:

All other endpoints not included in F1, F2 or F3 above are considered supportive and any statistical tests comparing treatments will be made without adjustment for multiplicity. The resulting p-values from these supportive analyses will be interpreted descriptively as summarizing the weight of evidence for a treatment difference and may suggest avenues for further exploratory analyses or generate formal hypotheses to be tested in future trials.

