9.2.5 Sample SAS code for rate of change in GCA score analysis

```
ods output ANOVA=ANOVA ParameterEstimates=Parms;  
proc reg data = subject_data ;  
  model GCA = VisitWk ;  
run ;Linear regression fit for individual subject data to calculate individual slope.
```

```
data weight;  
  set ANOVA(drop=Model DEPENDENT DF SS FVALUE PROBF);  
  weight=1/(1+MS);  
  if SOURCE='Error';  
run;
```

Two sample comparison:

```
proc glm;  
  class Trt;  
  model weighted_slope =trt;  
  lsmeans trt / pdiff CL;  
run;
```

where weighted slope=1/(1+MSE from linear regression fit)*slope.

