9.3.2 Simulation Methods

The baseline GCA score was generated as a normal random variable with a mean of 70 and standard deviation of 15 in both arms. An accept-reject approach was used to restrict the range of values to 55 to 85 (about 2/3 of the sample met this criterion). The records were divided into sets of 42 patients representing a clinical trial and randomly assigned to active or control groups in a 2:1 ratio using a Bernoulli distribution with parameter, $p = 2/3$. In this manner, approximately 3600 replications of a clinical trial dataset, each with 42 patients, were simulated.

In each replication, multivariate normal (MVN) data was generated for the repeated measures on the change in GCA score using SAS Proc SIMNORM with the following assumptions. Based on our Phase I/II data in the target population of interest, and under the alternative hypothesis, we assumed a 1 unit decline per month in GCA score in the untreated control arm. As up to 2 months may elapse between the baseline assessment and the start of idursulfase-IT treatment, a mean decline of 2 points at Month 13 would be expected if IT treatment was effective in stabilizing the decline. Therefore, under the alternative hypothesis the change in GCA data were generated assuming the following row vectors of mean changes and variances for the change from baseline corresponding to Months 4, 7, 10 and 13 in the control and active IT arms respectively:

Control: $\mu_c = (-4, -7, -10, -13)$, $\sigma^2 = (3^2, 5^2, 8^2, 10^2)$

Active: $\mu_a = (-2, -2, -2, -2)$, $\sigma^2 = (3^2, 5^2, 8^2, 10^2)$

This leads to the following row vector of mean treatment differences for the change from baseline (i.e. $\mu_a - \mu_c$): $\delta_a = (2, 5, 8, 11)$. The expected standard error of the mean difference at Month 13 is therefore $10(\sqrt{1/14+1/28})=3.3$. Similarly, under the null hypothesis of no treatment difference, MVN outcomes were generated with mean treatment differences $\delta_0 = (0, 0, 0, 0)$ with the same variances.

For each simulation, the data were generated using a first order auto-regressive (AR(1)) covariance structure with ij^{th} matrix element $\sigma_i\sigma_j\rho^{|i-j|}$, where the correlation between adjacent time points was set to $\rho = 0.80$. The covariance and correlation matrix was thus specified as displayed in [Tables A1](#) and [A2](#) respectively.

Table A1: Theoretical AR(1) Covariance Matrix for Repeated Measures (in change from baseline)				

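### The rate-of-change analysis in SAP 6.7.5.4 tests slope/(1+MSE) instead of the GCA slope it names, so its estimate and CI are not in points per week

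*SAP*

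**What the plan says.** The list of endpoints in SAP 4.1 gives one exploratory efficacy endpoint: "Slope estimate from the linear regression of GCA scores over time for each subject". SAP 6.7.5.4 repeats this and says the slopes will be compared between the arms by one-way ANOVA. The sentence that follows changes what is analysed: "The response variable in the ANOVA model is the weighted linear regression slope", with weight 1/(1+MSE).

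The code in SAP 9.2.5 leaves no doubt about the meaning. It regresses GCA on visit week for each patient, takes the error mean square, and fits PROC GLM with "model weighted_slope =trt", requesting LS means, their difference and confidence limits. Below the code it adds: "where weighted slope=1/(1+MSE from linear regression fit)*slope". There is no WEIGHT statement, no division by the sum of the weights, no back-transformation and no companion analysis of the unweighted slope.

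On eligibility, 6.7.5.4 says: "Only subjects with at least 3 available GCA scores will be included in this analysis". On status, SAP 8.5 says: "All other endpoints not included in F1, F2 or F3 above are considered supportive". The slope analysis is in none of the three families.

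**The concern.** The regression is on visit week, so the slope is in GCA points per week. Multiplying it by a patient-specific 1/(1+MSE) gives a quantity with no such unit. It also adds a bare 1 to a variance in squared points, so the result depends on the scale of the score. Two children who decline at the same rate contribute different values if one scatters more around his line.

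A weighted analysis would keep the slope as the response and use the weights to decide how much each patient counts. Here the weight changes the outcome itself and pulls every slope towards zero.

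At stake is the reading of the output. LS means, a difference and a CI produced under the title of a rate-of-change analysis will be taken as rates of GCA decline. The comparison could also respond to a difference in scatter between the arms when the rates do not differ.

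**Working it through.** **The plan's own figure.** The SAP gives no figure for the slope analysis, so there is none to reproduce directly. The sample-size statement that supplies two of the inputs (32:16, SD 11.6) does reproduce. For a difference of 11, SD 11.6, 2:1 allocation and two-sided 5%, 14 controls and 42 patients are needed. Then 42/0.90 = 46.7, so 47 against the stated 48. Power is 81.8% at 28.8:14.4 evaluable.

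**Single patient.** The analysed value is slope/(1+MSE). For a child losing 0.25 points per week:

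- MSE 1: -0.25/2 = -0.125
- MSE 16: -0.25/17 = -0.015
- MSE 36: -0.25/37 = -0.007

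**True slope difference under Appendix III.** SAP 9.3.2 gives mean changes at Weeks 16, 28, 40, 52 of (-4, -7, -10, -13) for control and (-2, -2, -2, -2) for active. Baseline is placed at Week 0 with change 0 (an assumption). The five times have mean 27.2 and sum of squared deviations 1644.8.

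- Control: -411.2/1644.8 = -0.250 points per week
- Active: -54.4/1644.8 = -0.033
- Difference: 356.8/1644.8 = 0.217

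**Simulation on those inputs.** SDs are 3, 5, 8, 10 with AR(1) correlation ("where the correlation between adjacent time points was set to" 0.80). They are used as given and also multiplied by 11.6/10 = 1.16, because SAP 4.2 "assumes a common standard deviation for the change from baseline of 11.6 points". There were 20,000 trials per scenario with complete data, and a pooled two-sample t-test, which is what the one-way ANOVA amounts to with two arms.

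| Scenario | Plain slope: difference, power | slope/(1+MSE): difference, power |
|---|---|---|
| SD 10, 32:16 | 0.217, 94-95% | 0.038, 72% |
| SD 11.6, 32:16 | 0.217, 86-87% | 0.031, 58-59% |
| SD 11.6, 29:14 | 0.217, 82-83% | 0.031, 54-55% |

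The ranges are the spread over repeated runs. The shrinkage is 0.217/0.038 = 5.7-fold and 0.217/0.031 = 7.0-fold. At SD 11.6 the mean weight is about 0.15, which accounts for most of it. The median 95% CI is 0.003 to 0.057. No simulated CI contained 0.217; plain-slope CIs covered it 95% of the time.

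**Type I error, same scatter in both arms.** The planned test rejects in 4.2 to 4.8% of trials, so it is not inflated.

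**Identical mean slopes, scatter differing by arm.** The documents give neither a residual SD by arm nor a between-patient slope SD, so these inputs are assumptions: common mean slope -0.25 per week, slope SD 0.05 to 0.20, 32:16, either arm noisier.

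| Residual SDs | Planned test rejects, over slope SD 0.05 to 0.20 |
|---|---|
| 3 and 3.5 | 5-13% |
| 3 and 4, control noisier | 24, 19, 15, 11% |
| 3 and 4, IT noisier | 30, 27, 23, 19% |
| 3 and 6, control noisier | 80, 73, 61, 45% |
| 3 and 6, IT noisier | 84, 79, 72, 63% |

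Plain slopes reject in 2 to 10% across the same cases. This happens because the product has mean roughly (common slope) × (mean weight). If the common slope is not zero and the mean weight differs by arm, the product means differ.

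**Would a WEIGHT statement repair it?** A patient with five scores has 3 residual df, and one with three scores has 1. With weights that unstable, ANOVA on the slope with weight 1/(1+MSE) rejects in about 12 to 13% of trials under the Appendix III nulls and about 10 to 18% across the assumed cases.

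**The case against.** The strongest reply has four parts.

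*The size is model-dependent.* The sevenfold figure needs every visit's SD multiplied by 1.16, which neither SAP 4.2 nor 9.3.2 does; on the Appendix III SDs as printed it is 5.7-fold. More generally, it depends on within-patient scatter, which no document states. In a random-slope model with Week 52 SD held at 11.6 and assumed residual SDs of 0.5, 1, 2, 3 and 5, the reported difference is 0.183, 0.127, 0.064, 0.038 and 0.017, a shrinkage of 1.2- to 13-fold. Power for the product is then 95, 90, 74, 67 and 54% against 87 to 89% for plain slopes. This stands: the loss of power is conditional and disappears if scatter is very small. A residual SD of 1 point or less around a child's line is, however, hard to credit for a cognitive test score.

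*Zero coverage is not separate evidence.* It measures the CI against a quantity that the product does not estimate. That is fair; it restates the change of estimand.

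*The false-positive case is assumed.* The SAP works with common variances, and the highest rejection rates need residual SD to double in one arm. In the mildest case (3 and 3.5, control noisier, slope SD 0.20) the excess all but vanishes. This also stands, and the result should be read as a possibility.

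*Little depends on it.* The analysis is exploratory and descriptive. The primary MMRM already gives differences in GCA points at every visit, and protocol 10.5.4 plans a random-coefficients slope comparison if appropriate. That limits the consequence but does not correct the analysis. The SAP neither describes the protocol's model nor lists it as dropped, and SAP 7.2 records only that a rate-of-change analysis was added, without a reason for the multiplier.

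**Conclusion.** The concern holds. That the planned response is not the named endpoint follows from the formula alone and needs no simulation: the text of 6.7.5.4 and the code in 9.2.5 agree on the product. The size is an illustration. Under Appendix III-type inputs with complete data, the reported difference is about one sixth to one seventh of the true difference in slopes, and power falls by roughly 20 to 30 percentage points. With equal scatter in both arms the error is towards a smaller apparent effect, with type I error kept. Only if scatter differs by arm around a non-zero common slope can the test signal a difference in rates that is not there. The primary MMRM, the key secondary test and the error-controlled families are untouched. The correction should be made because this is the SAP's only named exploratory efficacy endpoint and its output would be easy to misread.

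**What to change.** In SAP 6.7.5.4 and 9.2.5, make the unweighted slope the response (model slope = trt) and delete the multiplier; the LS-mean difference and CI are then in GCA points per week. Alternatively, fit the random-coefficients model of protocol 10.5.4 with a treatment-by-time term, which uses every patient's available scores without the three-score rule. Adjustment for GCA class and baseline GCA is optional. Do not transfer 1/(1+MSE) to a WEIGHT statement, given the rejection rates shown above. SAP 7.2 should say which slope analysis replaces or supplements the protocol's model. The cost is a few sentences and a few lines of code; data collection and trial conduct do not change.

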6.8 Analysis of Safety

All safety analyses will be descriptive, no statistical testing will be performed. All analyses described below refer to the pivotal study; safety data from the separate substudy will be listed due to small number of patients expected.

6.8.1 Adverse Events

AEs will be recorded throughout the study and at early termination. AEs and medical conditions will be coded using the MedDRA version 16.1 or higher.

Treatment emergent adverse event (TEAE) for control group is defined as all AEs occurring on or after the date of randomization and on or before the EOS visit. TEAE for IT-treatment group is defined as all AEs occurring on or after the date of the first IDDD implant surgery or first dose (whichever is earlier) and on or before the EOS visit (+ 30 days) or 2 weeks after the removal of the last IDDD (whichever is later). In general, an AE will be deemed TEAE if it cannot be definitively categorized by the available components (day, month, year) of the AE onset date with respect to the date of the randomization or the date of intervention (the date of the first IDDD implant surgery or first dose [whichever is earlier]). Summaries for the following AE categories will be presented:

1. Patients who experienced no AEs,
2. Patients who experienced at least one AE
3. Patients who discontinued due to an AE(s)
4. Patients who died
5. Patients who experienced at least one serious adverse event (SAE),
6. Patients who experienced at least one severe AE,
7. Patients who experienced at least one IV Elaprase infusion-related adverse event
8. Patients who experienced at least one idursulfase-IT-related adverse event
9. Patients who experienced at least one IT Treatment Regimen-related adverse event (i.e., related to one or more of the following: study drug, IDDD, device surgical procedure, and IT-administration process)
10. Patients who experienced at least one IDDD surgical procedure-related adverse event
11. Patients who experienced at least one IDDD-related adverse event
12. Patients who experienced at least one IT Administration Process-related adverse event

The AE categories 1-7 will be presented by each treatment group for patients in the Safety Population, while the AE categories 8-12 will be presented by each treatment group for patients in the Safety Population who received idursulfase-IT. IT administration process-related AEs will be summarized by IT administration method (LP or IDDD) as well. The AE categories 10-11 will be presented for patients in the Safety Population with the device implanted. The number and proportion of patients, and the number of corresponding AEs will be summarized in overall summary tables. In addition, the number and percentage of patients having any treatment-emergent AE within the AE categories 2, 5, 7-12 and the number of corresponding AEs will be displayed by MedDRA system organ class (SOC), preferred term (PT) and treatment group. The most common treatment-emergent AEs which happened in >10% patients in either treatment group will also be summarized by SOC and PT. The most common non-serious treatment-emergent AEs which happened in >5% patients in either treatment group will also be summarized by SOC and PT.

The number and percentage of patients having any treatment-emergent AE, and the number of corresponding AEs will be summarized by MedDRA SOC, PT and severity.

The number and percentage of patients having any treatment-emergent AE, and the number of corresponding AEs will be summarized by relationship to IV Elaprase, idursulfase-IT, and at least one IT treatment regimen, and summarized by MedDRA SOC and PT.

Furthermore, listings of all the AEs of categories 3-6 will be provided if applicable.

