10.7.1 Adverse Events

Adverse events will be recorded throughout the study and at early termination. Adverse events and medical conditions will be coded using the Medical Dictionary for Regulatory Activities (MedDRA) version 16.0 or later. Adverse events occurring on or after randomization and on or before the follow-up visit (scheduled 7 days after EOS Visit) will be summarized by treatment group, both overall and within system organ class (SOC) by preferred term. A summary of adverse events related to study drug will be presented. An adverse event will be considered related if indicated to be “possibly,” “probably,” or “definitely” related. A separate tabulation of IV Elaprase infusion-related adverse events will also be presented by treatment group. Adverse events will be tabulated by severity (mild, moderate, severe) and treatment group. In addition, those events which resulted in death or were otherwise classified as serious will be summarized and presented in a separate listing.

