10.7.8 Concomitant Medications/Therapies

Concomitant medications are defined as all medications taken on or after the time of the randomization and on or before the last follow-up date (scheduled 7 days after EOS Visit). Concomitant medications will be mapped using the World Health Organization Drug Dictionary (WHO-DD) and summarized by the therapeutic class and preferred term for each treatment group. Concomitant therapies will be mapped using the MedDRA Version 16.0 or higher and summarized by the SOC and preferred term for each treatment group.

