6.8.7 Concomitant Medications

Concomitant medications for control group are defined as all medications taken on or after the date of randomization and on or before the EOS visit. Concomitant medications for IT-treatment group are defined as all medications taken on or after the date of the first IDDD implant surgery or first dose (whichever is earlier) and on or before the EOS visit (+ 30 days) or 2 weeks after the removal of the last IDDD (whichever is later).

Concomitant medications will be coded using the WHO Drug Dictionary Version September 2013 or higher. Concomitant medication use will be summarized by the Therapeutic Class and Preferred Term for each treatment group for the Safety Population.

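### The SAP counts adverse events and concomitant treatments over different calendar periods in the two arms, replacing the protocol's common window without listing or explaining the change

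*SAP*

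**What the plan says.** **Protocol.** Section 10.7.1 tabulates by treatment group the events falling "Adverse events occurring on or after randomization and on or before the follow-up visit (scheduled 7 days after EOS Visit". It makes no distinction between arms. Section 10.7.8 gives concomitant medications the matching span, "on or after the time of the randomization and on or before the last follow-up date", again for both arms. Section 7.14.5.1 sets AE observation from consent to the follow-up evaluation 7 (±2) days after EOS for patients who complete.

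**SAP.** Section 6.8.1 defines a treatment-emergent AE separately by arm:

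- Control: "for control group is defined as all AEs occurring on or after the date of randomization and on or before the EOS visit".
- IT, start: "on or after the date of the first IDDD implant surgery or first dose (whichever is earlier".
- IT, end: "on or before the EOS visit (+ 30 days) or 2 weeks after the removal of the last IDDD (whichever is later".

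Section 6.8.7 follows the same pattern. Control medications are "all medications taken on or after the date of randomization and on or before the EOS visit", and IT medications use the surgery-or-dose start and the extended end. Section 6.8.8 repeats this for therapies.

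**Where the windows are used.** SAP 6.8.1 shows AE categories 1 to 7 by arm in the Safety Population and plans tables by system organ class and preferred term by arm. It adds common-event tables triggered when a term exceeds 10%, or 5% for non-serious events, in either arm. The medication and therapy tables are also by arm. Section 6.8 states that safety analysis is descriptive, without tests.

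**Disclosure.** The modification history (SAP 2.1) records that the definitions in 6.8.1, 6.8.7 and 6.8.8 were modified. SAP 7.2, which lists changes from the protocol's planned analyses, does not include them. No reason is given in either place.

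**The concern.** The untreated arm is the randomized reference for the safety of the IT regimen. A by-arm incidence table is readable only if both columns cover the same part of follow-up, or if person-time is taken into account. The SAP plans no exposure-adjusted AE rate, so the columns have to match by construction, and here they do not.

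Two stretches of time are affected.

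- **Randomization to surgery.** Control events count and IT events do not. Both arms receive weekly Elaprase in this interval, so category 7 (Elaprase infusion-related AEs) omits about two to three scheduled infusions (14/7 = 2, 21/7 = 3) in one arm only.
- **After EOS.** Protocol 8.4.1 and 8.4.2 put both arms through general anesthesia and a lumbar puncture for intracranial pressure at EOS. An event starting afterwards is treatment-emergent in IT but not in control, so the table loses its reference data for a procedure that the arms share.

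With about 16 controls (Protocol 5.1), one patient is 1/16 = 6.25%. A single excluded control event can therefore decide whether a non-serious term passes the 5% trigger in the control column.

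**Working it through.** **Inputs.** Day 0 is randomization. EOS is Week 52, or 13 months of 28 days (Protocol 4.1). Surgery is Week 2 + 7 days, so Day 14 to 21 (Protocol 7). The follow-up contact is EOS + 7 (±2) days. Window rules are those of Protocol 10.7.1 and SAP 6.8.1. Lengths are inclusive: end day − start day + 1.

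**Reproducing the plan's interval.** 13 × 28 = 364 and 52 × 7 = 364, so EOS falls on Day 364.

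**Window lengths, patient completing on schedule**

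| Window | Calculation | Days | Ratio to SAP control |
|---|---|---|---|
| Protocol, either arm | 371 − 0 + 1 | 372 (370 to 374 with ±2 days) | – |
| SAP control | 364 − 0 + 1 | 365 | 1.00 |
| SAP IT, surgery Day 14 | 394 − 14 + 1 | 381 | 1.044 |
| SAP IT, surgery Day 21 | 394 − 21 + 1 | 374 | 1.025 |
| SAP IT, surgery Day 14, collection ends EOS + 7 | 371 − 14 + 1 | 358 | 0.98 |
| SAP IT, surgery Day 21, collection ends EOS + 7 | 371 − 21 + 1 | 351 | 0.96 |

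The last two rows are needed because Protocol 7.14.5.1 ends routine observation at the follow-up contact. A later event is recorded only if the investigator raises it with the sponsor.

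**Change from the protocol window.** Control loses its last 7 days (371 − 364). IT loses the first 14 to 21 days after randomization and nominally gains 30 − 7 = 23 days after the follow-up contact.

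**Less typical patients**

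- First dosed by lumbar puncture at Week 4 (Day 28) with no earlier surgery: 394 − 28 + 1 = 367 days, or 371 − 28 + 1 = 344 if collection ends at EOS + 7.
- Device removed after EOS: the removal rule lengthens the window only when removal is more than 30 − 14 = 16 days after EOS. Removal at EOS + 60 (assumed) closes the window at Day 364 + 74 = 438, giving 438 − 14 + 1 = 425 days, ratio 1.16.
- Early withdrawal with EOS at Day 120 (assumed) and surgery at Day 14: control 121 days; IT 150 − 14 + 1 = 137 days, ratio 1.13.

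**Effect of length alone.** At an assumed constant rate of 0.5 first events per patient-year, the proportion with an event is 1 − exp(−0.5 × days/365.25). That is 39.3% for 365 days, 40.6% for 381 and 38.2% for 351. Length alone moves the figure by about one percentage point, in either direction.

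**Effect of the periods counted.** The mismatch in calendar coverage remains whichever collection rule applies. Before surgery, 14 to 21 days count in control and none in IT. After EOS, no days count in control and at least 7 in IT where the follow-up contact takes place.

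**The case against.** Starting a treatment-emergent definition at first intervention, with a tail that covers device removal, is coherent, and extra post-EOS time in the IT arm works against the product. Stopping control at EOS also avoids attributing to the control arm events that arise once those patients begin IT treatment in the extension. The version history discloses that the text changed. Safety is descriptive, and AEs in categories 3 to 6 (discontinuations, deaths, serious and severe events) are also listed individually.

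Much of this stands. An IT-specific window does no comparative harm in categories 8 to 12, which are confined to IT-treated or implanted patients. Extension entry is a real complication, since Protocol 8.5.1 waives the follow-up call for patients who enroll within its window. But one end rule applied to both arms would deal with it. It does not call for zero days after EOS in one arm and at least 30 in the other, and it does not explain the different start dates.

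A reader might infer more than the documents support:

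- **That the IT window is in effect about 4% longer, biasing against IT.** This needs capture to EOS + 30 days, which the protocol does not routinely provide; otherwise the IT window is 2 to 4% shorter.
- **That a definite number of controls lose an event.** The documents give no post-EOS event rate. Onsets on the day of EOS still count, and losing one event does not alter the any-AE count for a patient who had another.
- **That an IT-randomized patient with neither surgery nor dose has no window.** Safety is analyzed by treatment received (SAP 6.2), so such a patient would plausibly be grouped with control, although the SAP does not say so.
- **That every safety table is affected.** Laboratory and ECG summaries, for example, follow scheduled visits or post-baseline status.

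**Conclusion.** The concern holds in a limited form. SAP 6.8.1, 6.8.7 and 6.8.8 depart from the protocol's common window, and the by-arm AE, medication and therapy tables cover different periods in the two arms. For a patient completing on schedule, the net difference runs from 14 days shorter in IT (351 against 365) to 16 days longer (381 against 365), depending on surgery date and how far collection extends. The size is small and the direction is not established. The stronger defect is the coverage mismatch before surgery and after EOS. No type I error or efficacy conclusion is touched.

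Assumptions: EOS exactly on Day 364 (±7 days is allowed), surgery on Day 14 to 21, and the category 1 to 7 summaries read as using the treatment-emergent window under which SAP 6.8.1 lists them. The text difference is certain; its numerical effect on the tables cannot be known from the documents. It should be corrected before the safety tables are produced.

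**What to change.** 1. In SAP 6.8.1, 6.8.7 and 6.8.8, use randomization to the follow-up contact (EOS + 7 days) in both arms for every between-arm AE, medication and therapy table, in line with Protocol 10.7.1 and 10.7.8.
2. State one end rule, identical in both arms, for patients who enter the extension before that contact, for example the earlier of extension enrollment and the follow-up contact.
3. Keep the surgery/first-dose window only for IT-only device, procedure and IT-related tables. Note there that routine AE collection under this protocol ends at the follow-up contact, so coverage to EOS + 30 days or removal + 2 weeks may be incomplete.
4. List any remaining departure, with its reason, in SAP 7.2.

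The cost is SAP wording and one additional flag variable. No new data are needed, because AEs are already collected from consent to the follow-up contact where that contact takes place, and item 2 covers patients for whom it is waived.
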